2. In general, the window for each visit is \pm 3 days unless otherwise specified.
3. For women of reproductive potential, a urine or serum pregnancy test will be performed within 72 hours prior to first dose of trial treatment. If urine pregnancy results cannot be confirmed as negative, a serum pregnancy test, performed by the local study site laboratory, will be required. Pregnancy tests (serum and/or urine tests) should be repeated if required by local guidelines.
4. Coagulation factors (PT/INR and aPTT) should be monitored closely throughout the trial for any subject receiving anticoagulant therapy.
5. Laboratory tests for screening are to be performed within 10 days prior to the first dose of trial treatment.
6. After Cycle 1, lab samples can be collected up to 72 hours prior to the scheduled time point. Laboratory results must be known and acceptable prior to dosing.
7. The initial tumor imaging will be performed within 30 days prior to the first dose of trial treatment. Scans performed as part of routine clinical management are acceptable for use as the screening scan if they are of diagnostic quality and performed within 30 days prior to the first dose of trial treatment. On-study imaging will be performed every 6 weeks (42 -7 days) after the first dose of trial treatment or more frequently if clinically indicated. The timing for imaging studies should follow calendar days and should not be adjusted for delays in cycle starts or extension of MK-3475/afatinib cycle frequencies. The same imaging technique should be used in a subject throughout the trial. CT including the chest, abdomen and pelvis or PET-CT is required for the baseline assessment.
8. Provide documentation of the subject's tumor EGFR mutation from a CLIA certified laboratory.
9. MK-3475 can be administered for up to 2 years. For the dose de-escalation and Cohort (Arm) A (concurrent afatinib and MK-3475) both drugs will be administered as outlined in this protocol starting with cycle #1. For cohort B. MK-3475 will be initiated with cycle #1 and afatinib will commence in combination with MK-3475 starting with cycle #3.
10. Tumor biopsy for immune and EGFR biomarker analysis will be performed prior to Cycle 1 of treatment either on archival tissue or fresh biopsy (within 60 days). Repeat biopsy will be performed prior to initiation of cycle 3 (42 days (-7 days))

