7.1.2.6 Tumor Imaging and Assessment of Disease

For the purposes of this study, patients should be re-evaluated for response after cycle 2 (6 weeks) and then every 2 cycles (6 weeks). In addition to a baseline scan, confirmatory scans should also be obtained at least 4 weeks following initial documentation of objective response.

RECIST version 1.1* will be used in this study for assessment of tumor response. While either CT or MRI may be utilized, as per RECIST 1.1, CT is the preferred imaging technique in this study.

* As published in the European Journal of Cancer:

- PET-CT At present, the low dose or attenuation correction CT portion of a combined PET-CT is not always of optimal diagnostic CT quality for use with RECIST measurements. However, if the site can document that the CT performed as part of a PET-CT is of identical diagnostic quality to a diagnostic CT (with IV and oral contrast), then the CT portion of the PET-CT can be used for RECIST measurements and can be used interchangeably with conventional CT in accurately measuring cancer lesions over time. Note, however, that the PET portion of the CT introduces additional data which may bias an investigator if it is not routinely or serially performed.
- Conventional CT and MRI This guideline has defined measurability of lesions on CT scan based on the assumption that CT slice thickness is 5 mm or less. If CT scans have slice thickness greater than 5 mm, the minimum size for a measurable lesion should be twice the slice thickness. MRI is also acceptable in certain situations (e.g. for body scans).

Definitions

Evaluable for toxicity. All patients will be evaluable for toxicity from the time of their first treatment with *MK-3475 and afatinib*.

Evaluable for objective response. Only those patients who have measurable disease present at baseline, have received at least one cycle of therapy, and have had their disease re-evaluated will be considered evaluable for response. These patients will have their response classified according to the definitions stated below. (Note: Patients who exhibit objective disease progression prior to the end of cycle 1 will also be considered evaluable.)

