From the time of treatment allocation through 30 days following cessation of treatment, all adverse events must be reported by the investigator. Such events will be recorded at each examination on the Adverse Event case report forms/worksheets. The reporting timeframe for adverse events meeting any serious criteria is described in section 7.5. The investigator will make every attempt to follow all subjects with non-serious adverse events for outcome.

Adverse events will not be collected for subjects during the pre-screening period (for determination of archival tissue status) as long as that subject has not undergone any protocol-specified procedure or intervention. If the subject requires a blood draw, fresh tumor biopsy etc., the subject is first required to provide consent to the main study and AEs will be captured according to guidelines for standard AE reporting.

All adverse events, serious and non-serious, will be collected, documented and reported to the

company supporter by the investigator on the appropriate CRFs / SAE reporting forms (BI and Merck SAE report form).

For each adverse event, the investigator will provide the onset date, end date, CTC AE grade, treatment required, outcome, seriousness, and action taken with the investigational drug. The investigator will determine the relationship of the investigational drug to all AEs as defined below.

Adverse events with onset within first administration of afatinib therapy and 28 days after last administration of afatinib will be considered as on treatment. All AEs, including those persisting after end of study treatment must be followed up until they have resolved or have been sufficiently characterized or the principal investigator decides to not further pursue them. Serious and non-serious adverse events occurring later than 28 days after last administration of trial drugs will only be reported in case they are considered drug-related or trial (procedure) related.

7.5.1 Definition of an Overdose for This Protocol and Reporting of Overdose to Merck

For purposes of this trial, an overdose of pembrolizumab will be defined as any dose of 1,000 mg or greater (>5 times the indicated dose). No specific information is available on the treatment of overdose of MK-3475. Appropriate supportive treatment should be provided if clinically indicated. In the event of overdose, the subject should be observed closely for signs of toxicity.

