7.5.3 Immediate Reporting of Adverse Events to Merck and BIPI

7.5.3.1 Serious Adverse Events

A serious adverse event is any adverse event occurring at any dose or during any use of Merck's product that:

- Results in death;
- Is life threatening;
- Results in persistent or significant disability/incapacity;
- Results in or prolongs an existing inpatient hospitalization;
- Is a congenital anomaly/birth defect;
- Is another important medical event

Note: In addition to the above criteria, adverse events meeting either of the below criteria, although not serious per ICH definition, are reportable to the Merck in the same timeframe as SAEs to meet certain local requirements. Therefore, these events are considered serious by Merck for collection purposes.

- Is a new cancer (that is not a condition of the study);
- Is associated with an overdose.

Refer to Table 12.7 for additional details regarding each of the above criteria.

For the time period beginning when the consent form is signed until treatment allocation, any serious adverse event, or follow up to a serious adverse event, including death due to any cause other than progression of the cancer under study (Section 7.2.3.3 for additional details) that occurs to any subject must be reported within 2 working days to Merck Global Safety if it causes the subject to be excluded from the trial, or is the result of a protocol-specified intervention, including but not limited to washout or discontinuation of usual therapy, diet, placebo treatment

or a procedure.

Progression of the cancer under study is not considered an adverse event unless it results in hospitalization or death.

For the time period beginning at treatment allocation, through 90 days following cessation of treatment, or 30 days following cessation of treatment if the subject initiates new anti-cancer therapy, whichever is earlier, any serious adverse event, or follow up to a serious adverse event, including death due to any cause other than progression of cancer under study (reference Section 7.5.4 for additional details), whether or not related to Merck product, must be reported within 2 working days to Merck Global Safety.

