8.0 STATISTICAL ANALYSIS PLAN

8.1 Statistical Analysis Plan Summary

This is a phase I/Ib study. A minimum of 9 patients, if trial is terminated early due to unacceptable toxicity and a maximum of 38 patients (18 patients in the dose de-escalation cohort plus 10 in each of the two expansion cohorts) are anticipated for this trial. Analysis of safety and biomarkers will be limited to patients who receive active treatment.

The dose de-escalation phase will establish a MTD recommended dose of MK-3475 in combination with lead in MK-3475 followed by the combination or concurrent afatinib/MK-3475.

We plan to enter 3 patients at Dose Level 0. If 0/3 or 1/3 patients experience a DLT on level 0, an additional 3 patients will be accrued to Level 0, where 2 or more DLTs will terminate that study arm and we will proceed to dose level -1.

If 2 or more patients have DLTs at level 0, patients will be accrued at level -1. If 1/3 patients experience a DLT on level -1, an additional 3 patients will be accrued to Level -1, where 2 or more DLTs will require termination of that study arm while 1 DLT out of 6 will result in proceeding with dose level -1 as the MTD for the dose expansion cohorts.

If 2 or more patients have DLTs at level -1, patients will be accrued at level -2. If 1/3 patients experience a DLT on level -2, an additional 3 patients will be accrued to Level -2, where 2 or more DLTs will require termination of the study while 1 DLT out of 6 will result in proceeding with dose level -2 as the MTD for the dose expansion cohorts.

The phase I de-dose escalation portion of the trial will be closed when the maximum tolerated dose level (MTD) or dose level 0 is reached and six patients have been treated at that dose level.

Please see section 5.1.4.2 for further details.

All patients at a given dose level who have not experienced DLT, must be observed for a minimum of 21 days or until completion of their first cycle of therapy before the dose level can be escalated. Treatment will continue in an individual patient at the same dose level if no DLT is observed and if benefit is observed. There will be no dose escalation allowed for an individual patient.

The recommended phase II dose (RP2D) will be determined by the overall assessment of the MTD and toxicities observed in the de-dose escalation and dose expansion portion of this study.

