The baseline assumption is that single agent afatinib yields a response rate of 10% in this setting, and a response rate of 10% or less would not warrant further study. A response rate of 40% or greater would justify further study with a larger sample size. With 10 patients enrolled in cohort A expansion arm, we will declare this combination lacking promise if fewer than 3 patients respond, and potentially worthy of further study if 3 or more patients respond. If the true response rate is 10%, the chance of having 3 or more patients respond is 7%. If the true response rate is 40%, the

chance of having 3 or more patients respond is 83%.

If 3 or more patients respond, the response rate, toxicity, and progression-free survival will be evaluated to decide if larger randomized studies are warranted in this disease. Descriptive summaries will be provided for each of these summary measures (numbers and proportion responding, number and proportion with specific type and grade of toxicities, Kaplan-Meier plot and life-table summary of progression-free survival.) As stated earlier, a “pick the winner” approach between cohort A and cohort B based on toxicity: RR, PFS and changes in PDL1 expression will decide which dosing scheme to take further. It is assumed that a true RR >40% would be sufficient to recommend such development, provided safety and tolerability are also acceptable.

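### The on-treatment window for adverse events is tied to afatinib alone, so in Cohort B it leaves out the six-week MK-3475 lead-in, and Section 8.1 does not say which window the A-versus-B toxicity comparison uses

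*Combined protocol and SAP*

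**What the plan says.** Section 8.1 lists descriptive summaries, among them the "number and proportion with specific type and grade of toxicities". It then describes a pick-the-winner "approach between cohort A and cohort B based on toxicity: RR, PFS and changes in PDL1 expression will decide which dosing scheme to take further". No start point, window or denominator is given for toxicity in that choice. The same section says: "Analysis of safety and biomarkers will be limited to patients who receive active treatment".

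Section 7.5 contains two rules. For reporting: "From the time of treatment allocation through 30 days following cessation of treatment, all adverse events must be reported by the investigator". For classification: "Adverse events with onset within first administration of afatinib therapy and 28 days after last administration of afatinib will be considered as on treatment".

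Section 7.1.2.6 has a third: "All patients will be evaluable for toxicity from the time of their first treatment with" MK-3475 and afatinib.

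For Cohort B, footnote 9 of the flow chart in Section 6.1 says that "afatinib will commence in combination with MK-3475 starting with cycle #3". Section 2.1 gives the lead-in as two cycles, or six weeks, of MK-3475 alone. In Cohort A both drugs start on Day 1 of Cycle 1.

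**The concern.** A window that opens with the first afatinib dose suits a regimen in which afatinib is given from the start. It does not suit Cohort B, where MK-3475 is the only drug for the first six weeks. Taken literally, every adverse event in that period is not on treatment, although the patient is receiving a study drug.

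The clearest case is pneumonitis. Table 5 in Section 5.1.5.3 requires permanent discontinuation of MK-3475 for Grade 3-4 pneumonitis, and Table 6 discontinues afatinib if interstitial lung disease is confirmed. A Cohort B patient with this event in the lead-in may well never start afatinib. The window then never opens, and the event never counts as on treatment. Yet it is exactly the kind of toxicity by which an MK-3475 lead-in should be judged.

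Two things are at stake: the safety description of Cohort B in a trial whose primary objective is safety and tolerability, and the toxicity criterion in the choice between the two schemes. With open-label data, a window left undefined can also be settled after the results are known.

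**Working it through.** **The plan's own figures.** The documents give no number for the toxicity comparison. The only computable figures in Section 8.1 belong to the response rule for Cohort A. With X binomial and n = 10, P(X ≥ 3) is 0.0702 at a 10% response rate and 0.8327 at 40%. These match the stated 7% and 83%, and this point does not affect them.

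**Start points side by side.** The lead-in lasts 2 × 21 = 42 days.

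| Rule | Cohort A | Cohort B | Lead-in events in B |
|---|---|---|---|
| 7.5, reporting | allocation | allocation | included |
| 7.5, on treatment | Cycle 1 Day 1 | Cycle 3 Day 1, or never if afatinib is not started | excluded |
| 7.1.2.6, evaluable for toxicity | Cycle 1 Day 1 | Cycle 1 Day 1 if either drug suffices; Cycle 3 Day 1 if both are needed | depends on the reading |
| 8.1, safety analysis | all actively treated, no start time | all actively treated, no start time | patient included; event window not stated |

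In Cohort A the rules practically coincide. In Cohort B they differ by up to 42 days.

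**What one patient does.** Suppose 1 of 10 treated Cohort B patients has Grade 3 pneumonitis in the lead-in and never starts afatinib.
- From first dose of either drug, all treated: 1/10 = 10%.
- Afatinib window, all treated: 0/10 = 0%.
- Afatinib window, afatinib recipients only: 0/9 = 0%.

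The same event on the same study day in a Cohort A patient counts as 1/10 under every rule.

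**How often this could arise.** The documents give no event rates, so the hazards here are assumptions. Let h be the monthly hazard of a relevant MK-3475 event and take 42 days as 1.38 months, ignoring early stopping. Then p = 1 − exp(−1.38h), and the chance of at least one lead-in event among 10 patients is 1 − (1 − p)^10.
- h = 0.02: p = 2.7%, chance 24%.
- h = 0.05: p = 6.7%, chance 50%.

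So an omitted event is plausible, but across this range it is no more likely than not.

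**The closing end.** The window closes 28 days after the last afatinib dose even if MK-3475 goes on, which Section 5.4 can allow. That applies to both cohorts, but it is a further reason to tie the window to either drug. Section 7.5 reports all events to 30 days, so 28 and 30 days also need aligning.

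**The case against.** The strongest reply is that the afatinib window is a classification in a recording section, and Section 8 never uses the term on treatment. The analysis rule is the sentence in Section 8.1 on actively treated patients, and lead-in patients meet it. Nor is anything lost from collection. Events are reported from allocation. Serious events are reportable from allocation "through 90 days following cessation of treatment, or 30 days following cessation of treatment if the subject initiates new anti-cancer therapy". Pneumonitis of Grade 2 or higher is an event of clinical interest in the Appendix 12.9 guidance. New related serious events are reviewed monthly by the monitoring committee (Section 10.5). All of this stands. A reader might infer that lead-in toxicity will go unrecorded, or that the analysis is bound to omit it; the documents support neither. What remains is that Section 7.5 states an explicit rule that is wrong for Cohort B, and Section 8.1 does not set it aside.

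A reader might also infer that a raw proportion is the wrong measure because afatinib exposure differs by design, and that exposure-adjusted or fixed-window rates are needed. The documents do not support that either. The stated aim is to choose a dosing scheme. Patients who stop during the lead-in, and so never meet afatinib toxicity, are part of what that scheme does. An all-treated proportion is a legitimate summary for that purpose.

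Fixed windows from first study dose could even widen the contrast. Assume a monthly afatinib hazard of 0.25 to 0.40 in its first month and 0.02 after, and an MK-3475 hazard of 0.02 to 0.05. At six weeks Cohort A would show 1 − exp(−(0.25 + 0.02 × 0.38 + 0.02 × 1.38)) = 25% to 1 − exp(−(0.40 + 0.02 × 0.38 + 0.05 × 1.38)) = 38%. Cohort B, still without afatinib, would show 3% to 7%.

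Finally, the comparison is sequential, non-randomized, 10 against 10 and descriptive, with toxicity one of several criteria. The summary quoted from Section 8.1 is introduced for the decision on larger studies, and the pick-the-winner sentence names no toxicity measure of its own. That limits the weight of the point.

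**Conclusion.** The point holds in a limited form and is minor. The on-treatment definition in Section 7.5 is anchored to the wrong drug for Cohort B. It conflicts with reporting from allocation and sits badly with the safety population in Section 8.1, while the evaluability sentence in Section 7.1.2.6 can be read either way. Because the rules coincide at the start for Cohort A, the conflict over the start point bears on one cohort only.

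This conclusion rests on the text alone and needs no assumed rate. Its size does. Each affected patient moves a Cohort B proportion by 10 points, and the 24% to 50% chance of at least one such event depends wholly on assumed hazards. If the analyst counts every event in every treated patient from first dose, which is the natural reading of Section 8.1, the effect is nil. The raw proportion itself is not at fault.

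**What to change.** In Section 7.5, define on-treatment toxicity as onset from the first dose of either study drug to 30 days after the last dose of either study drug, and align the following 28-day sentence with it. In Section 7.1.2.6, start evaluability for toxicity at the first dose of either drug. In Section 8.1, add one sentence stating that this window, with all treated patients as denominator, is used for the A-versus-B toxicity table. Leave the longer reporting period for serious events and events of clinical interest as it is.

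Optionally, split Cohort B events into lead-in and combination periods, and give the number of patients who never started afatinib.

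The cost is about one sentence per section. Onset dates (Section 7.5) and per-cycle treatment forms (Section 10.9) are already collected, so no new data are needed. The only downside is that Cohort B's stated toxicity may be slightly higher than under the afatinib window.

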8.2 Correlative Statistical Analysis Plan

Plasma EGFR-mutant DNA/RNA levels, PDL1 expression by IHC at baseline and in repeat biopsy specimens as well as the other EGFR and immune biomarkers proposed will be evaluated in exploratory manner. A focus is on comparison between changes in PD-L1 expression comparing arm A (concurrent afatinib/MK-3475) and arm B (lead in MK-3475). Descriptive associations with response rate and PFS will be performed. All molecular and other secondary evaluations will be considered for exploratory analyses and in view of the limited sample-size and the exploratory nature of these analyses, any p-values reported will not be adjusted for multiple comparisons, and any such analyses will be stated carefully as being hypothesis-generating.

Standard descriptive methods will be used to summarize the baseline levels and changes in baseline levels will allow us to examine whether observed patterns are consistent with hypothesized patterns. If the combination is not found to have sufficient activity, these patterns may help explain the lack of activity. If sufficient activity is found, then patients who experience an objective response will be compared to those who did not in terms of these correlates.

9.0 LABELING, PACKAGING, STORAGE AND RETURN OF CLINICAL SUPPLIES

9.1 Investigational Product: MK-3475

The investigator shall take responsibility for and shall take all steps to maintain appropriate records and ensure appropriate supply, storage, handling, distribution and usage of investigational product in accordance with the protocol and any applicable laws and regulations.

Clinical Supplies will be provided by Merck at no cost to subjects as summarized below.

Product Descriptions

Product Name & Potency	Dosage Form
MK-3475 100 mg/ 4mL	Solution for Infusion

Instructions on preparation are provided with Merck pharmacy manual.

